8.4. Pharmacokinetics

Blood will be collected and used for the measurement of plasma concentrations of GB004, and metabolites of GB004 (glucuronide [GBD242] and glucoside [GBD243]) as specified in the SoA (Section 1.3.1 – PCP and Section 1.3.2 – OLE). On the visit day, the subject should be instructed to take the dose at the site following the predose blood sample draw. If a subject withdraws early from the study, a blood sample may also be taken, if possible.

Colon tissue samples will be collected during flexible sigmoidoscopy/colonoscopy and may be used for measuring concentration of GB004.

Additionally, stool samples may be analyzed for levels of GB004.

Samples may also be used for assay development and characterization of potential metabolites of GB004.

Drug concentration information that may unblind the study will not be reported to investigative sites or blinded personnel.

8.5. Pharmacodynamics and Biomarkers

Blood, stool, and colonic biopsy samples should be collected as designated in the SoA (Section 1.3.1 – PCP and Section 1.3.2 – OLE) and may be used for exploratory assessment of TE/PD biomarkers, eg, histology, c-reactive protein (CRP), fecal calprotectin, fecal lactoferrin, gene expression, and immunohistochemistry, e.g. HIF-1 α , EGLN1-2-3, etc.

Samples may be stored at a facility selected by the Sponsor, to enable further analysis of biomarker responses to GB004, for a maximum of 8 years (or according to local regulations) following the last subject's last visit for the study.

Residual blood, and urine samples may be stored for potential future identification of factors or profiles that correlate with measures of response to GB004.

Please refer to the study specific Central Laboratory Manual for PD biomarker details.

8.6. Pharmacogenetic

Pharmacogenetic (PGx) analyses may be performed on any bio-sample from subjects who have consented for PGx sampling. Subject confidentiality will be maintained.

Suitable bio-samples should be collected from all subjects, where permitted by law and local authorities. Those subjects who are prohibited from participating in the PGx research by law and/or local authorities, and those subjects providing a written (documented) opt-out, may still participate in the study.

9. STATISTICAL CONSIDERATIONS

9.1. Statistical Hypotheses

9.1.1. Placebo-Controlled Period

The PCP is designed to demonstrate the superiority of each GB004 treatment group to placebo on the primary endpoint of the proportion of subjects with clinical remission at PCP Week 12. The PCP is also designed to demonstrate the superiority of each GB004 treatment group to placebo on the primary endpoint of the proportion of subjects with clinical remission at PCP Week 36.

9.1.2. OLE

The purpose of the OLE period is to evaluate the long-term safety and tolerability of GB004. No formal statistical hypotheses are being tested.

9.2. Sample Size Determination

9.2.1. Placebo-Controlled Period

A total sample size of approximately 195 subjects (approximately 65 per treatment group, randomized 1:1:1, with stratification by systemic corticosteroid use at baseline [yes/no]) is estimated to provide approximately 80% power to detect a difference of 20.4% between each GB004 treatment group and placebo for the primary endpoint of proportion of subjects with clinical remission at PCP Week 12 based on a chi-squared test at an 0.050 two-sided level of significance. This assumes the proportion of subjects with clinical remission at PCP Week 12 is 10% in the placebo group and 30.4% in each GB004 treatment group and a dropout rate by PCP Week 12 of approximately 8%. Subjects with missing clinical remission status at PCP Week 12 will be considered as having not met the primary endpoint.

Using the same sample size assumptions as above for the primary endpoint of proportion of subjects with clinical remission at PCP Week 12 (ie, a difference of 20.4% between each GB004 treatment group and placebo, with a 10% proportion in the placebo group), there will be approximately 80% power for the secondary endpoint of the proportion of subjects with clinical remission at PCP Week 36 based on a chi-squared test at an 0.050 two-sided level of significance. Subjects with missing clinical remission status at PCP Week 36 will be considered as having not met the endpoint.

9.2.2. OLE

There is no formal sample size calculation for this period of the study. This is an extension of the PCP. Subjects must complete at least 12 weeks of treatment in the PCP prior to dosing in the OLE. Therefore, the maximum number of subjects potentially eligible to participate in the OLE will not be greater than the total number of subjects randomized in the PCP (approximately 195 subjects).

9.3. Populations for Analyses

9.3.1. Placebo-Controlled Period

The following major analysis populations are defined for the PCP:

- Intent-to-treat (ITT) Population: All subjects who are randomized and receive at least 1 dose of IP, with subjects grouped according to randomized treatment.
- Safety Population: All subjects who receive at least 1 dose of IP, with subjects grouped according to their actual treatment.

9.3.2. OLE

The following major analysis populations are defined for the OLE:

- OLE Safety Population: All subjects who receive at least one dose of IP in the OLE.
- GB004-treated Safety Population: All subjects who receive at least one dose of GB004 in PCP and/or OLE.

9.4. Statistical Analyses

Three separate formal statistical analyses will be performed:

- The PCP Week 12 Analysis will be conducted after all subjects either complete the PCP Week 12 visit or withdraw from the study prior to completion of the PCP Week 12 visit. This analysis will evaluate endpoints at or up through PCP Week 12.
- The PCP Final Analysis will be conducted after all subjects either complete the PCP or withdraw from the study prior to completion of the PCP; This analysis will evaluate all PCP endpoints.
- The OLE Final Analysis will be conducted after all subjects either complete the OLE period or withdraw from the study prior to completion of the OLE period.

The study will be unblinded to the Sponsor at the time of the PCP Week 12 Analysis. Therefore, the PCP will be double-blind through PCP Week 12 and will remain blinded to subjects, investigators, and site staff throughout the PCP.

In general, continuous variables will be summarized using the number of subjects with non-missing data, mean, standard deviation, standard error (where appropriate), median, minimum, and maximum. Categorical variables will be summarized using counts and percentages.

For the PCP Week 12 Analysis and the PCP Week 36 Analysis, baseline will be defined as the last non-missing value prior to first dose of IP in the PCP. For the OLE Analysis, GB004 baseline will be defined as the last non-missing value prior to the first dose of GB004 in the study.

This section is a summary of the planned statistical analyses of the primary, secondary, and safety endpoints.

9.4.1. PCP Week 12 Analysis

9.4.1.1. Efficacy Analyses

The ITT population will be utilized for efficacy analyses.

Primary Endpoint

The primary endpoint of the proportion of subjects with clinical remission at PCP Week 12 will be compared between each GB004 treatment group and placebo by a Cochran-Mantel Haenszel (CMH) chi-squared test ([Mantel, 1959](#)) stratified by systemic corticosteroid use at baseline (yes/no) with a two-sided 0.050 level of significance. If stratum cell sizes are too small based on the Mantel-Fleiss criterion ([Mantel, 1980](#)), Pearson's chi-squared test will be used instead.

For the comparison of each GB004 treatment group versus placebo, the p-value from the CMH chi-squared test will be reported, along with the estimated Mantel-Haenszel common odds ratio across strata and corresponding 95% CI. The number and proportion of subjects meeting the primary endpoint and corresponding 95% Wilson (Score) CIs ([Wilson, 1927](#)) will be summarized by treatment group. The absolute difference in proportion between each GB004 treatment group and placebo will also be summarized, with the 95% CI for the absolute difference based on the Newcombe continuity-corrected method ([Newcombe, 1998](#)).

In the primary analysis of the primary endpoint, subjects with missing clinical remission status at PCP Week 12 will be considered as having not met the primary endpoint. The primary endpoint will also be analyzed using various other methodological approaches for handling subjects with missing data as sensitivity analyses.

Secondary Endpoints

The secondary endpoints of the proportion of subjects with clinical response at PCP Week 12, the proportion of subjects with histologic remission at PCP Week 12, the proportion of subjects with endoscopic improvement at PCP Week 12, and the proportion of subjects with mucosal healing at PCP Week 12 will be analyzed using the same approach as the primary endpoint. Histologic remission at PCP Week 12 and mucosal healing at PCP Week 12 will be evaluated among subjects with Baseline lamina propria neutrophils and neutrophils in epithelium RHI subscores > 0 .

These secondary endpoints will be assessed at a two-sided level of significance of 0.050 for the comparison of each GB004 treatment group and placebo.

9.4.1.2. Safety Analyses

All safety analyses will be performed using the Safety Population. Safety data will be listed by subject.

Safety analyses will be focused on treatment-emergent AEs, defined as an AE with onset on or after the start of study treatment. The incidence of AEs will be summarized by treatment group, including the incidence by system organ class and preferred term, severity, and relationship to study drug, the incidence of SAEs, the incidence of AEs that lead to discontinuation of study drug, and the incidence of AEs that lead to withdrawal from study.

9.4.2. PCP Final Analysis

The PCP Final Analysis will be performed using the same methodological approaches as the PCP Week 12 Analysis.

9.4.3. OLE Final Analysis

The OLE Safety population will be used as the primary analysis population for safety analyses, which will be based on data from the OLE period.

Select safety analyses will summarize the safety experience of all subjects treated with GB004 in the PCP or the OLE period, using the GB004-Treated Safety population, with data combined across the PCP and OLE.

Additionally, in order to inform assessment of whether there appear to be any new or worsening safety signals in the OLE period, select safety analyses will summarize the placebo-controlled safety experience in the PCP side-by-side with the continuing GB004 safety experience in the OLE period (using subjects in the OLE Safety population who were previously treated with GB004).

Safety analyses will be focused on TEAEs, defined as an AE with onset on or after the start of study treatment in the respective analysis. The incidence of AEs will be summarized by treatment

group, including the incidence by system organ class and preferred term, severity, and relationship to study drug, the incidence of SAEs, the incidence of AEs that lead to discontinuation of study drug, and the incidence of AEs that lead to withdrawal from study. The incidence of AEs and SAEs by system organ class and preferred term may also be presented by time intervals. Incidence rates of AEs adjusted for time on study (eg, number of subjects per 1000 subject-years) may also be presented.

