- Anti-nuclear antibody
- Anti-smooth muscle antibody
- Type 1 anti-liver kidney microsomal antibodies
- Quantitative total immunoglobulin G (IgG) or gamma globulins
- Serum acetaminophen assay
- Serum creatine phosphokinase (CPK)
- Lactate dehydrogenase (LDH)
- Complete Blood Count with differential
- Obtain blood sample for pharmacokinetic (PK) analysis

The above assessments will be conducted only if required.

APPENDIX 3. ADVERSE EVENTS: DEFINITIONS AND PROCEDURES FOR RECORDING, EVALUATING, FOLLOW-UP, AND REPORTING

Definition of AE

AE Definition

• An adverse event, AE, is any untoward medical occurrence in a subject or clinical study subject whether or not considered related to the IP.• NOTE: An AE can therefore be any unfavorable and unintended sign (including an abnormal laboratory finding), symptom, or disease (new or exacerbated) temporally associated with the use of IP.

Events Meeting the AE Definition

• Any abnormal laboratory test results (hematology, clinical chemistry, or urinalysis) or other safety assessments (eg, ECG, radiological scans, vital signs measurements), including those that worsen from baseline, considered clinically significant in the medical and scientific judgment of the Investigator (ie, not related to progression of underlying disease).• Exacerbation of a chronic or intermittent pre-existing condition including either an increase in frequency and/or intensity of the condition.• New conditions detected or diagnosed after IP administration even though it may have been present before the start of the study.• Signs, symptoms, or the clinical sequelae of a suspected drug-drug interaction.• Signs, symptoms, or the clinical sequelae of a suspected overdose of either IP or a concomitant medication. Overdose per se will not be reported as an AE/SAE unless it is an intentional overdose taken with possible suicidal/self-harming intent. Such overdoses should be reported regardless of sequelae.• “Lack of efficacy” or “failure of expected pharmacological action” per se will not be reported as an AE or SAE. Such instances will be captured in the efficacy assessments. However, the signs, symptoms, and/or clinical sequelae resulting from lack of efficacy will be reported as SAE if they fulfil the definition of an SAE.

Events NOT Meeting the AE Definition

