- If a subject dies during participation in the study or during a recognized follow-up period, the Investigator will provide the Sponsor with a copy of any postmortem findings including histopathology.
- New or updated information will be recorded in the originally completed eCRF.
- The Investigator will submit any updated SAE data to the Sponsor within 24 hours of receipt of the information.

Reporting of SAEs**SAE Reporting to the Sponsor via an Electronic Data Collection Tool**

- The mechanism for reporting an SAE to the Sponsor will be the electronic data capture system.
- If the electronic system is unavailable, then the site will contact the Sponsor's Medical Monitor (or designee) in order to report the event and submit the paper SAE report form via the contacts below within 24 hours.
- The site will enter the SAE data into the electronic system as soon as it becomes available.
- After the study is completed at a given site, the electronic data collection tool will be taken off-line to prevent the entry of new data or changes to existing data.
- If a site receives a report of a new SAE from a study subject or receives updated data on a previously reported SAE after the electronic data collection tool has been taken off-line, then the site can report this information via contact to the Sponsor's Medical Monitor (or designee) and submitting the paper SAE report form via the contacts below.
- Contacts for SAE reporting can be found in Study Manual.

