3.1.2. Placebo-Controlled Period Final Analysis

For subjects who consent only to version 1.0 of the protocol, all data reported will be included in the PCP Final Analysis.

For subjects who consent to version 2.0 of the protocol, data to be included in the PCP Final Analysis will generally be dependent on whether a subject is dosed in the OLE as follows:

- For subjects not dosed in the OLE, all data reported will be included in the PCP Final Analysis.
- For subjects dosed in the OLE, all data up through the date and time (where ascertainable) of first dose of OLE study treatment will be included in the PCP Final Analysis.

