9. SAFETY EVALUATION

9.1. Adverse Events

Verbatim AE terms will be coded to an SOC and PT using MedDRA Version 24.0 or later.

All analyses of AEs will be based on the principle of treatment emergence. An AE is considered to be treatment-emergent as follows:

- PCP Week 12 Analysis:
 - For subjects who consent only to protocol version 1.0 and for subjects who consent to protocol version 2.0 and withdraw from PCP at or prior to PCP Week 12: AEs that start on or after the first dose of PCP study treatment.
 - For subjects who consent to protocol version 2.0 and do not withdraw from PCP at or prior to PCP Week 12: AEs that start on or after the first dose of PCP study treatment through the PCP Week 12 nominal visit (if date of PCP Week 12 nominal visit is non-missing) inclusive or through Day 85 (if date of PCP Week 12 nominal visit is missing) inclusive.

- PCP Final Analysis:
 - For subjects not dosed in the OLE: AEs that start on or after the first dose of PCP study treatment;
 - For subjects dosed in the OLE: AEs that start on or after the first dose of PCP study treatment and prior to the first dose of OLE study treatment.

In general, if the treatment emergence of an AE is not clear due to a missing or incomplete AE start date/time and/or missing start time for first dose of PCP study treatment, the AE will be considered to be treatment-emergent for the given analysis, unless the non-missing portions of the AE start date/time and the end date/time and the date of first dose of PCP study treatment indicate otherwise.

For subjects who consent to version 2.0 of the protocol, in cases where an AE has a non-missing start date equal to the date of PCP Week 12, the AE will be considered treatment emergent for the PCP Week 12 Analysis if it is reported on the appropriate AE eCRF intended to capture AEs through PCP Week 12. If the date of PCP Week 12 is missing, then the target day for PCP Week 12 (Day 85) will be utilized for the purpose of determining treatment emergence.

In cases where an AE has a non-missing start date equal to the date of first dose of OLE study treatment, but the AE start time and/or time of first dose of OLE study treatment is missing, the AE will be considered treatment-emergent to the PCP if it is reported on the appropriate AE eCRF intended to capture AEs in the PCP.

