In general, whenever a tabular summary of AEs is mentioned in this SAP, it is intended that the tabular summary is in reference to treatment emergent AEs, even though “treatment emergent” may not be explicitly mentioned. By-subject data listings of AEs will include all events regardless of treatment emergence.

Counting will be at the subject level for each level of summarization (eg, any AE, SOC, and PT), with subjects experiencing more than one AE counted only once. For summary of AEs by severity, subjects will be counted once at the highest severity reported at each level of summarization. AEs that are missing severity will be presented in summary tables as “Missing”. AEs that are missing relationship to study treatment will be presented in summary tables as “Related”.

The following AE summaries will be presented:

- Overall Summary of AEs, showing the number and percentage of subjects with an AE; a moderate or severe AE; a severe AE; a serious adverse event (SAE) including UC SAEs (defined as the PT of ‘Colitis ulcerative’); an SAE excluding UC SAEs; a treatment-related AE; a treatment-related SAE; an AE leading to dose reduction, dose interruption, or discontinuation of PCP study treatment; an AE leading to dose reduction; an AE leading to dose interruption; an AE leading to discontinuation of PCP study treatment; an AE leading to withdrawal from PCP; and an AE resulting in death.
- Incidence of AEs by SOC and PT
- Incidence of AEs by PT

- Incidence of AEs $\geq 5\%$ in Any Treatment Group by PT
- Incidence of AEs $\geq 2\%$ Higher in Either GB004 Treatment Group Relative to Placebo by PT
- Incidence of SAEs by SOC and PT including UC SAEs
- Incidence of SAEs by SOC and PT excluding UC SAEs
- Incidence of AEs by SOC, PT, and maximum severity
- Incidence of Treatment-Related AEs by SOC and PT
- Incidence of AEs Leading to Dose Reduction of PCP Study Treatment by SOC and PT
- Incidence of AEs leading to Dose Reduction of PCP Study Treatment by PT
- Incidence of AEs Leading to Dose Interruption of PCP Study Treatment by SOC and PT
- Incidence of AEs Leading to Dose Interruption of PCP Study Treatment by PT
- Incidence of AEs Leading to Discontinuation of PCP Study Treatment by SOC and PT
- Incidence of AEs Leading to Discontinuation of PCP Study Treatment by PT
- Incidence of AEs Leading to Withdrawal from PCP by SOC and PT
- Incidence of AEs Leading to Withdrawal from PCP by PT
- Incidence of AEs Resulting in Death by SOC and PT

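### The OLE counts a TEAE by onset date only, so an adverse event carried over from the PCP that worsens on open-label GB004 may not enter the OLE primary endpoint

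*Protocol*

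**What the plan says.** **Definitions.** Protocol 3.2 makes TEAE incidence the OLE primary endpoint. Protocol 9.4.3 then says: "Safety analyses will be focused on TEAEs, defined as an AE with onset on or after the start of study treatment in the respective analysis". For the PCP, Protocol 9.4.1.2 uses the same idea, "defined as an AE with onset on or after the start of study treatment". SAP 9.1 limits PCP events in subjects who go on to be dosed in the OLE to "AEs that start on or after the first dose of PCP study treatment and prior to the first dose of OLE study treatment". All three rules turn on the start date. None mentions worsening.

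**Recording.** Protocol Appendix 3, on follow-up of AEs and SAEs, says: "New or updated information will be recorded in the originally completed eCRF". The same appendix lists among events that meet the AE definition: "Exacerbation of a chronic or intermittent pre-existing condition including either an increase in frequency and/or intensity of the condition".

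**Severity and data cut.** In the severity summaries of SAP 9.1, "subjects will be counted once at the highest severity reported at each level of summarization". SAP 3.1.2 states which data the final PCP analysis uses: "For subjects dosed in the OLE, all data up through the date and time (where ascertainable) of first dose of OLE study treatment".

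**Populations.** Protocol 9.3.2 and 9.4.3 provide an OLE safety analysis and a pooled analysis of everyone who received GB004 in either period. SAP 1 places the detailed OLE methods in a separate SAP, which is not among the documents.

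**The concern.** At OLE entry all subjects go to GB004 480 mg BID. That is a first exposure for former placebo subjects and a doubling of the planned daily dose for former QD subjects (480 mg to 2 × 480 = 960 mg). Protocol 6.5.1 also allows a subject whose dose was reduced in the PCP, possibly for a treatment-related AE, to enter the OLE at the reduced or the full dose. Some subjects may therefore bring an ongoing AE into a period of higher exposure.

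If that AE then becomes more severe or serious, it is an unwanted on-treatment change of the kind the OLE exists to describe. A rule based on start date alone assigns the event to the period in which it began. Whether the worsening is counted then depends on whether the site happens to open a second record, and the documents give the site no rule. Two sites could follow the same text and produce different OLE TEAE counts from the same clinical course.

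**Working it through.** No sample size or error rate enters this point, and the plan states no figure to reproduce. The check applies the written rules to one hypothetical event.

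**Assumed event.** A mild AE starts on Day 200. The first OLE dose is on Day 253, which is the Week 36 target day in SAP 3.2 (36 × 7 + 1 = 253). The AE becomes severe on Day 280. Days 200 and 280 are invented for illustration.

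**Rules applied.**
- PCP TEAE: start date from the first PCP dose to before Day 253 (SAP 9.1).
- OLE TEAE: start date on or after Day 253 (Protocol 9.4.3).
- Pooled GB004 TEAE: start date on or after the first GB004 dose. This is my reading of treatment start in the respective analysis, and it matches the GB004 baseline in Protocol 9.4. For a former placebo subject it is Day 253; for a former GB004 subject it is Day 1.

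| Subject | How worsening is recorded | PCP | OLE TEAE | Pooled GB004 TEAE |
|---|---|---|---|---|
| Placebo, then GB004 | one record, updated | counted* | none | none |
| GB004 throughout | one record, updated | counted* | none | severe |
| Placebo, then GB004 | new record on Day 280 | mild | severe | severe |
| GB004 throughout | new record on Day 280 | mild | severe | severe (maximum) |

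*The PCP severity is mild if the SAP 3.1.2 cut is applied to the severity field. It would be severe only if the field had been overwritten without a date and the cut could not be applied.

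**What the table shows.**
1. With one updated record the OLE column is empty for both subject types, whichever way the footnote is resolved. The start date of Day 200 precedes Day 253, and nothing else in the definition can bring the event in.
2. In the pooled column only the former placebo subject loses the event.
3. With a new record all three analyses behave as one would wish.

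**Which record would be made?** The follow-up sentence in Appendix 3 favours one updated record, but it is general: it names neither severity nor worsening, and it sits beside text on supplemental tests and postmortem findings. The exacerbation item favours a new AE, but it speaks of pre-existing conditions and does not say that an AE which arose during the PCP is one. SAP 9.1 does refer to a PCP-specific AE form, since an event dated on the day of the first OLE dose, with a time missing, belongs to the PCP "if it is reported on the appropriate AE eCRF intended to capture AEs in the PCP". That settles ownership of a start date. It does not cover an event that continues into the OLE and changes.

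**Scope.** Under Protocol 8.3.6, worsening UC that is not an SAE is not reported as an AE at all, so the gap concerns other AEs and UC events that reach SAE status.

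**The case against.** The strongest reply is that the OLE has its own SAP, which may already deal with worsening, and that Protocol 9.4 calls itself a summary. That is fair, so it cannot be asserted that such events will in fact be missed. But the protocol's OLE definition is explicit, and a repair made only in the OLE SAP would depart from it.

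Second, a site may properly open a new AE for an exacerbation, and Protocol 9.4.3 would then count it. This also stands, and it is why the finding is conditional on how the event is recorded.

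Third, the aim about new or worsening signals is attached to a side-by-side comparison in subjects previously on GB004, and it concerns signals in aggregate, not single events. True; but a worsening signal can appear as rising severity of existing events, and the stated definition does not see that.

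Fourth, other safeguards exist: SAEs are reported within 24 hours, the DRC reviews unblinded safety data, and the OLE tests no formal hypothesis. These protect subjects and limit the inferential stakes. They do not correct the endpoint summary.

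A reader might go further and infer that the later severity is charged to the PCP arm, perhaps to placebo. The documents do not support this as a rule. SAP 3.1.2 ends PCP data at the first OLE dose, and safety tables group subjects by actual treatment, not randomised treatment (Protocol 9.3.1, SAP 4.3). It could happen only through an undated, overwritten severity field, which would be an operational failure. A reader might equally infer that sites are told to write worsening into the first record; the follow-up sentence does not say so.

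**Conclusion.** The point holds in a limited form. The OLE TEAE definition in the protocol omits worsening, and no recording rule in either document fills the gap. Where a single updated record is kept, a PCP-onset AE that becomes more severe or serious on open-label GB004 is not an OLE TEAE. For former placebo subjects it is also absent from the pooled GB004-treated TEAE summaries; for subjects on GB004 in the PCP it remains in the pooled analysis.

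The size cannot be estimated. The documents give no rate of AEs ongoing at OLE entry and no rate of later worsening. The only bounds are ceilings on who is exposed to the rule: about 195 subjects for the OLE (Protocol 9.2.2) and about 65 randomised to placebo for the pooled analysis. These are not estimates of events missed.

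The conclusion rests on two assumptions: that the unseen OLE SAP does not already add worsening, and that the pooled analysis starts at the first GB004 dose. It casts no doubt on the controlled PCP comparison as the SAP defines it.

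**What to change.** 1. **Protocol 9.4.3, carried into the OLE SAP:** define an OLE TEAE as an AE with onset, or an increase in severity, or a change to serious, on or after the first OLE dose. Use the same wording for the pooled analysis, counted from the first GB004 dose.
2. **Protocol Appendix 3:** when an AE ongoing at the first OLE dose worsens, require either a new record with its own start date or dated severity changes within the existing record. Say which, so that sites do the same thing.
3. Dated severity also lets the existing SAP 3.1.2 cut be applied to the PCP severity tables, so no new PCP rule is needed.

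The cost is one clause in the protocol and OLE SAP, an eCRF completion note, and a round of queries on AEs ongoing at OLE entry. A new record adds entries for one clinical course, but SAP 9.1 counts at subject level; if the OLE SAP does the same, pooled incidence is not inflated. No dose, visit or efficacy test changes.
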